PROTOCOL TITLE

Validation of a point-of-care screening tool for children with sickle cell disease

PRINCIPAL INVESTIGATOR:

ADDRESS:

TELEPHONE:

EMAIL:

SIGNATURE: _____

ABSTRACT

Background: Sickle cell disease (SCD) is the commonest genetic disorder in Nigeria, affecting up to 150,000 newborns per year. Given the high frequency of the HbS gene and the large population of affected children, high infant and under-5 mortality, it is estimated that SCD contributes at least 6% of all childhood mortality and of those affected, only 10% in sub Saharan Africa (SSA) are likely to reach adolescence. The clinical course of SCD is characterized by acute and chronic complications, which may be severe, leading to significant morbidity and mortality. Timely diagnosis is key to prevent or manage these complications. However, current diagnostic methods rely on laboratory systems that are expensive and time consuming or may even be unavailable.

General Aim: The primary study objective is to validate the HemeChip technology as a rapid, point-of care (POC) platform for screening SCD.

Methodology: This will be a single site cross-sectional study.

Expected Outcome: The validation of the HemeChip technology as an affordable, robust, easy-to-use POC platform for screening of sickle cell disease (SCD).

1. BACKGROUND

1.1 Introduction

Sickle cell disease (SCD) is a group of inherited disorders of haemoglobin (Hb) synthesis, first described in the medical literature by James Herrick in 1910. Each year about 300,000 infants are born with SCD, including more than 200,000 cases in sub-Saharan Africa alone.¹ In Nigeria, alone, there are over 150,000 of these children born annually and it is estimated that between 50-90% of these children die before their fifth birthday.² Overall, in the region, 6% of all childhood mortality in children less than 5 years of age is due to SCD complications and infections. Vaso occlusive crisis and anemia are serious complications of SCD, with infection often being the major cause of hospitalizations, crisis and death.

SCD is caused by a point mutation in the sixth codon of the beta globin chain that produces normal Hb (HbA). This substitution of hydrophilic glutamic acid with hydrophobic valine produces sickle Hb (HbS), which is abnormally polymerized at low oxygen conditions causing sickling. Abnormal polymerization of HbS affects red cell membrane properties, shape, and density, and subsequent critical changes in inflammatory cell and endothelial cell function.³ The clinical consequences of SCD include painful crises, widespread organ damage, and early mortality.

1.2 Problem statement

Current standard practices for diagnosing SCD are high performance liquid chromatography (HPLC) and bench-top Hb electrophoresis. These two approaches, however, require trained personnel and state-of-the-art facilities, both of which may be lacking in many parts of sub-Saharan Africa where the disease is most prevalent.⁴ These laboratory methods also carry significant costs which may be unaffordable for most patients.

1.3 Relevance and Innovation

HemeChip diagnostic system offers an original and innovative solution, leveraging a novel engineering approach, to point of care (POC) diagnosis of SCD. HemeChip

separates haemoglobin protein types in a miniscule volume of blood (1 μ L) on a piece of cellulose acetate paper that is housed in a micro-engineered chip with a controlled environment and electric field. Differences in Hb mobilities allow separation to occur within the cellulose acetate paper. A micro-engineered design and multiple layer lamination approach are utilized in fabricating the HemeChip. The design allows rapid manual assembly and results are available within a few minutes of performing the test. HemeChip can also integrate with a mobile user interface (e.g. iPhone, iPod), which shows the test result quantitatively and objectively on the screen. HemeChip can be used by anyone after a short (30 minute) training, eliminating the need for highly skilled personnel.

2. AIMS

2.1 General objective

The primary study objective is to validate the HemeChip technology as a novel, point-of care (POC) platform for screening SCD. The results obtained using the HemeChip will be compared to High Performance Liquid Chromatography (HPLC), and the sensitivity and specificity of the HemeChip will be determined.

2.2 Secondary objective

- i. To determine the acceptability of using the HemeChip for POC screening of SCD during clinical assessments.

3. LITERATURE REVIEW

Despite its recognition as a global public health problem, SCD remains a neglected health priority in many low- and middle-income countries. Ironically, the burden of haemoglobinopathies is projected to increase in the coming decades. By 2050, it is estimated that the proportion of sickle cell anaemia births in sub-Saharan Africa will be about 88% of the worldwide total, compared to 79% in 2010. This increase will be largely as a result of population growth and public health transition.⁵

The pathophysiology of SCD includes premature red cell haemolysis, vascular obstruction, endothelial damage, chronic inflammation and infarction. These result in acute and chronic complications such as severe anaemia, bone pain, stroke and end organ damage.^{6,7} Complications may begin during infancy particularly in individuals with homozygous disease. Newborn screening for SCD has been shown to be highly effective in reducing the morbidity and mortality associated with SCD, when linked to comprehensive healthcare services.^{8,9} National programs for routine, universal newborn screening for SCD are lacking in many African countries, Nigeria inclusive.¹⁰ Consequently, most children are diagnosed opportunistically, when they present to health facilities with clinical symptoms and signs suggestive of SCD.

Standard diagnostic testing for sickle cell disease include cellulose acetate or citrate agar electrophoresis (bench top electrophoresis), IEF, high performance liquid chromatography (HPLC), capillary electrophoresis and molecular analysis.¹¹

Bench top Hb electrophoresis: This is a laboratory method that can be done under alkaline or acidic conditions and with a variety of sieving materials such as gel or paper.¹² Under alkaline conditions, Hb types C, A2, S, F, and A have net negative charges and migrate towards the positively charged electrode forming visible bands that can be used to identify various Hb disorders. Although useful for the rapid screening of a small number of samples, its results may suffer from inaccuracies at low concentrations. Moreover, alkaline Hb electrophoresis has the disadvantage of having poor resolution between HbS and HbF, particularly in neonates who have high HbF levels, which may result in inaccurate identification of overlapping bands.

Isoelectric Focusing (IEF): IEF exploits the fact that the net charge of a protein varies with the pH of the surrounding medium. Utilizing this variation, proteins are separated based on their isoelectric points (pI), which can be defined as the point at which a protein possesses zero net charge. The technique uses an applied electric field across a gel medium with a fixed pH gradient, each Hb type becomes immobilized once it reaches its pI. IEF exhibits higher resolution than Hb electrophoresis, thus it is capable of distinguishing between a larger number of Hb variants. However, due to the larger number of bands that this higher resolution results in, IEF results are harder to interpret.^{12,13} IEF is also expensive and results can be inaccurate especially at low Hb concentrations. Despite these disadvantages, IEF is considered suitable for newborn screening since diagnosis is possible with very small sample volume or even an eluate from a dried blood spot.¹²

High Performance Liquid Chromatography (HPLC): HPLC separates a fluid into its components based on size and charge using cation exchange chromatography to identify the various Hb types in a blood sample. Unique aspects of this test are full automation and accurate quantification of the Hb levels. These machines are relatively expensive and are not readily available in developing countries.⁴ In resource rich countries like the US, HPLC has largely replaced Hb electrophoresis and IEF as the gold standard.

DNA Analysis: DNA-based assays can be used to detect the mutations in β globin that produce abnormal Hb.¹⁴ However, it is generally more expensive than the previously described methods and is most often used for prenatal testing rather than postpartum.¹⁵

HemeChip Technology: HemeChip technology offers an original and innovative solution, leveraging a novel engineering approach, to point-of-care diagnosis of SCD. The basis of HemeChip technology lies in Hb electrophoresis, in which Hb types C, A2, S, F, and A0 have net negative charges in an alkaline solution. Differences in Hb mobilities allow separation to occur within the sieving medium, cellulose acetate paper.

There is no POC device for SCD or any other Hb disorder screening on the market. Currently available tests require skilled technicians in central labs. In Africa, HPLC costs up to \$50 and takes 2-3 weeks to get the results. The National Institutes of Health in the United States has awarded a handful of innovation research grants in the past year to six small businesses to develop affordable POC diagnostic technologies for SCD (Correlia Bio., Rockland Immun., Daktari Diag., Silver Lake Res., Halcyon Biom., and Qoolabs). The vast majority of these companies rely on lateral flow immunoassays, which embody specific antibodies. Unlike the HemeChip technology, antibody based devices are specific to only a single disease, and would not work for different Hb disorders. Furthermore, the performance and reliability of lateral flow devices quickly degrade under uncontrolled environmental conditions in resource-limited countries.¹⁶

HemeChip technology is a low-cost, point-of-care translation of the electrophoresis method that has been well established, readily accepted by clinicians, and widely applied in SCD diagnosis for well over 40 years. HemeChip was clinically tested and successfully benchmarked against available standard methods (i.e., HPLC, bench-top electrophoresis) using 82 blood samples from 27 patients at University Hospitals, Cleveland, USA. HemeChip offers a \$2 screening test for SCD (and other Hb disorders), which takes 10 minutes to run. It is mobile and easy-to-use; it can be performed by anyone after a short (30 minute) training. The \$2 HemeChip based newborn screening can be overlaid on existing successful (WHO, UNICEF data) primary vaccination programs in sub-Saharan Africa, as a time-for-screening. Primary customers would be the front-line health care workers in government-established immunization programs and pediatric clinics in sub-Saharan Africa.

4. METHODOLOGY

4.1 Study design

This is a single site, cross-sectional study.

4.2 Study site

Study participants will be identified through the Community-Acquired Pneumonia and Invasive Bacteremia Disease study (CAPIBD) currently enrolling at three government hospitals in Kano, Nigeria to include Aminu Kano Teaching Hospital, Murtala Mohammed Specialist Hospital and Hasiya Bayero Pediatric Hospital.

Aminu Kano Teaching Hospital (AKTH) is one of the pioneer medical schools in northern Nigeria and provides tertiary referral service for several neighboring states. The 500 bed tertiary facility is located in the state of Kano and lies within the Sudan savannah belt. AKTH has a staff strength of 1,984 and serves as the teaching hospital for Bayero University Kano. The hospital provides health care for Kano and 5 neighboring states, which has a combined population of over 25 million people. AKTH receives regular power supply from the public grid and has both generator and battery backups. Murtala Muhammed Specialist Hospital (MMSH) and Hasiya Bayero Children's Hospital are affiliated government hospitals where faculty, residents and students from AKTH rotate to gain pediatric experience.

Murtala Mohammad Specialist Hospital is one of the pioneer hospitals in Nigeria. Established in 1924, it is reputed to be the second largest hospital in West Africa. It is located in the central city of Kano State and as such, caters for a majority of the estimated 10 million people in the State. The hospital has a staff strength of 1,917 out of which, there are about 97 medical doctors and 415 nursing staff. The outpatient clinics cater for an average of 30,000 patients monthly.

4.3 Subjects/study population

Subjects eligible for this study include children age 6 weeks to 60 months enrolled in CAPIBD from one of the three enrollment sites in Kano, Nigeria.

Inclusion/Exclusion criteria

Inclusion criteria:

Age 6 weeks to 60 months with one of the following true:

1. fever or hypothermia (Temp $\geq 38^{\circ}\text{C}$ or $\leq 36^{\circ}\text{C}$) Plus one of the following (prostration, excessive crying, poor feeding, altered consciousness, convulsion, difficulty breathing, profuse vomiting, diarrhea)
2. Rapid breathing (0-2months >60 breaths/min, 3-12months >50 breaths/min, 13-59 months > 40 breaths /min)

AND

3. Provision of signed and dated written informed consent by parent or guardian

Exclusion criteria:

1. Parent of child chooses to opt out of the study after initial consent.
2. Blood transfusion within 3 months of study enrollment.
3. Presence of condition or abnormality that in the opinion of the investigator would compromise the safety of the child or the quality of the data.

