4.4 Sample size estimate

Sample size is based on the known prevalence of SCD in Nigeria (SCD prevalence of 2.39% and a carrier rate of about 23%)¹⁹, using the following formula and a 95% confidence interval.¹⁷

1. Specify clinically acceptable values for the width of 95% confidence interval (CI), sensitivity (SN), specificity (SP), and the disease prevalence (P).
2. Calculate the number of patients with disease, defined as the sum of true positive cases (TP) and false negative cases (FN) using:

$$TP + FN = Z_{\alpha/2}^2 \frac{SN(1 - SN)}{W^2}$$

3. Calculate the sample size required to obtain the desired sensitivity as:

$$N1 = \frac{TP + FN}{P}$$

4. Calculate the number of patients without disease, defined as the sum of true negative cases (TN) and false positive cases (FP) using:

$$TN + FP = Z_{\alpha/2}^2 \frac{SP(1 - SP)}{W^2}$$

5. Calculate the sample size required to obtain the desired specificity as:

$$N2 = \frac{TN + FP}{P}$$

Where $Z_{\alpha/2}$ is a statistical constant having a value of 1.96 for 95% CI.

6. Select the required sample size as the greater of N1 and N2.

The calculations made for the HemeChip test sample size are summarized in Table 1 below:

Prevalence estimate	P	0.024
Width of the 95% CI: 10%	W	0.10
Sensitivity expected: 98%	SN	0.97
Specificity expected: 98%	SP	0.97
Statistical constant, 1.96 for 95% CI	Zalpha	1.96
Number with disease, True Positive + False Negative	TP+FN	11
Sample size required for sensitivity	N1	468
Number without disease, False Positive + True Negative	FP+TN	11
Sample size required for specificity	N2	11
FINAL SAMPLE SIZE (greater of N1 and N2)		468

Total maximum enrollment of 5,000 patients, age 6 weeks to 60 months identified through CAPIBD.

Procedure

The CAPIBD medical officer will introduce the study and ask if parent/caregiver is willing to participate. If yes, signed informed consent will be obtained and the subject assigned a unique identification number through CAPIBD. The clinical research assistant (CRA) assigned to the study will complete a questionnaire including demographic data and family information, and perform a heel or finger prick to obtain a blood sample for HemeChip and HPLC (page 12).

HemeChip Test

- a. Finger-stick or heel-stick blood sample (20 μ L) is mixed with deionized water for red blood cell lysis and the mixture allowed to set for 3 minutes.
- b. 65 μ L of a buffer solution is used to wet the paper inside the HemeChip.

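### Children with already known SCD are eligible and are pooled with new cases, so the reported PPV, yield and sensitivity need not describe the children a screening test is for

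*Combined protocol and SAP*

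**What the plan says.** Section 2.1 states the purpose: "The primary study objective is to validate the HemeChip technology as a novel, point-of care (POC) platform for screening SCD". Section 3 foresees use in immunisation programmes and paediatric clinics.

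Section 4.3 defines who enters: "Subjects eligible for this study include children age 6 weeks to 60 months enrolled in CAPIBD from one of the three enrollment sites". Fever or hypothermia with a further sign, or rapid breathing, is also required. Besides opt-out there are two exclusions, "Blood transfusion within 3 months of study enrollment" and "Presence of condition or abnormality that in the opinion of the investigator would compromise the safety of the child or the quality of the data". Neither names known SCD or an earlier haemoglobin test.

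Under Procedure in section 4.4 (Sample size estimate), the clinical research assistant "will complete a questionnaire including demographic data and family information, and perform a heel or finger prick to obtain a blood sample". No item on prior diagnosis is described, and the form itself is not shown. The HemeChip steps that follow do not say who performs them or whether that person is masked to the child's history. They do say that the result comes from the computer attached to the reader.

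Section 4.5 (Statistical analysis) defines sensitivity, specificity, PPV and NPV over all children, with HPLC as the standard and no split by prior diagnosis.

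**The concern.** A screening result is useful only in a child whose status is not yet known. Section 3 says that in the absence of routine newborn screening "most children are diagnosed opportunistically, when they present to health facilities with clinical symptoms and signs suggestive of SCD". A child of up to 60 months who attends hospital may therefore have been diagnosed at an earlier visit. Such a child is a true case for the accuracy calculation but not a screening candidate.

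Three things are at stake:

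- **PPV and yield.** Known cases raise the prevalence in the sample, so pooled PPV overstates what a positive result means among children not yet diagnosed. This follows from prevalence alone and needs no bias in the test.
- **Information on sensitivity.** Every known case leaves one fewer case that bears on screening.
- **Sensitivity itself.** Known and new cases may differ in age or severity, and an unmasked operator may know the answer beforehand. Either could move the pooled figure.

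**Working it through.** **Inputs from section 4.4 (Sample size estimate).** Prevalence P = 2.39% (0.024 in Table 1), a national figure; SN = SP = 0.97 as entered in Table 1 (the labels say 98%); W = 0.10; z = 1.96; N = 468; maximum enrolment 5,000.

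**Assumed.** f, the share of SCD cases already known, is not in the documents. The range 25% to 75% is used.

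**1. The plan's own figure.** TP + FN = 1.96² × 0.97 × 0.03 / 0.10² = 11.18. N1 = 11.18 / 0.0239 = 467.7, so 468 reproduces (465.8 with P = 0.024). Expected cases are 468 × 0.0239 = 11.2, or 5,000 × 0.0239 = 119.5 at the maximum.

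**2. Pooled PPV.** SN·P / [SN·P + (1 − SP)(1 − P)] = 0.02318 / (0.02318 + 0.02928) = 0.44.

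**3. PPV in children not previously diagnosed.** Removing known cases changes the prevalence to P_f = P(1 − f) / (1 − P·f), which goes into the same PPV formula. Specificity is unaffected by this step, because the children removed are all HPLC-positive. New cases are 11.2 or 119.5 times (1 − f).

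| f | P_f | PPV, not previously diagnosed | New cases at N = 468 | New cases at N = 5,000 |
|---|---|---|---|---|
| 0 | 2.39% | 44% | 11.2 | 119.5 |
| 25% | 1.80% | 37% | 8.4 | 89.6 |
| 50% | 1.21% | 28% | 5.6 | 59.8 |
| 75% | 0.61% | 17% | 2.8 | 29.9 |

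**4. Precision for new cases.** If all n new cases are detected, the exact 95% lower limit is 0.025^(1/n). This is 71.5% for n = 11, 63% for 8, 54% for 6 and 29% for 3. At the maximum enrolment it is 96% for n = 90 and 88% for n = 30.

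**5. How far sensitivity could move.** In the extreme case that every known case is called positive, pooled sensitivity is f + (1 − f)s, where s is sensitivity in new cases. With s = 0.90 (assumed) it reads 92.5%, 95% or 97.5%. With 11 cases one result moves sensitivity by 1/11 = 9.1 points, so a shift of this size could not be seen at 468.

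**6. Feasibility.** Enrolment for 11.18 new cases is 11.18 / [0.024(1 − f)] = 622, 932 or 1,864 at f = 25%, 50% or 75%. All are below 5,000.

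**The case against.** The strongest reply is that the study compares two measurements of haemoglobin type on the same child, and prior diagnosis does not change the haemoglobin in the sample. The reader and its computer give the result, which leaves an operator little room to steer it. The transfusion exclusion removes some known cases, and the investigator-opinion exclusion could remove more. Section 3 can also be read the other way: if diagnosis happens at presentation, hospital is where undiagnosed children are found. Finally, the PPV drop is prevalence arithmetic, and section 2.1 names only sensitivity and specificity.

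Much of this stands. The comparison with HPLC remains valid, and prior diagnosis is plausible, not established. But section 4.5 commits to PPV and NPV, the exclusions do not name known SCD, and case mix can differ even with an objective reader.

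A reader might go further in four ways that the documents do not support:

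- *The research assistant who takes the history also runs the chip and can repeat or adjust a discordant run.* No chip operator is named and no repeat or adjustment is described. Manual sample application without stated masking leaves the route open, no more.
- *Prior diagnosis is not recorded, so the problem cannot be corrected later.* The listed questionnaire content is not exhaustive and the form is not shown. Only the absence of a described item can be asserted.
- *Only 8 to 3 new cases will be available.* That holds at 468; the protocol also allows 5,000.
- *The 37%, 28% and 17% are shares of all positives in the study.* They are PPVs among children not previously diagnosed. As a share of all study positives, new true cases are 0.97 × 0.0239 × (1 − f) / 0.05247 = 33%, 22% and 11%.

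**Conclusion.** The concern holds as a gap between purpose and analysis. Known cases are eligible, no recording of prior diagnosis or masking is described, and every accuracy measure is pooled, although the aim is screening. The clearest effect is on PPV: 44% pooled against 37%, 28% or 17% where screening would apply. Those figures assume SN = SP = 0.97, that the national prevalence of 2.39% applies to these acutely ill children, and a known share of 25% to 75%. The documents give no such share; if it is near zero, the effect is negligible, but as described the analysis would not show which is the case.

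Inflated sensitivity is a possibility only. Neither operator influence nor a case-mix difference is shown, and the values in step 5 are scenarios. The change should be made because it is cheap and decides whether the results can be read as evidence about screening; its absence does not invalidate the accuracy comparison.

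**What to change.** 1. **Record.** At consent, the CAPIBD medical officer notes whether SCD or haemoglobin type is already known, and the result if so. This goes on an eCRF item separate from the research assistant's questionnaire. If the existing form already has such an item, move it there.
2. **Mask.** The item is not shown to whoever runs the chip until the HemeChip result is stored. Name that role in the HemeChip Test steps.
3. **Analyse.** In section 4.5, report sensitivity, specificity, PPV and NPV with exact intervals in children not previously diagnosed, next to the all-children figures. State in advance how a child with a known non-SCD haemoglobin type is classed.

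The cost is one eCRF item, a small change in who records it and when it is released, and one extra table. No child is excluded and follow-up does not change. The downside is fewer cases and a wider interval for the screening-relevant estimate.
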